NU Study Number: NU 16L04
Other Study Number: CA 209-801

STUDY SUMMARY

Title	Parallel proof of concept phase 2 study of nivolumab and metformin combination treatment in advanced non-small cell lung cancer with and without prior treatment with PD-1/PD-L1 inhibitors
Version	4.22.19 (Amendment 5)
Study Design	Phase II proof of concept study with two parallel groups
Study Center(s)	Northwestern University
Objectives	
Primary Objective: To assess anti-tumor activity of the combination treatment of metformin with nivolumab in patients with non-small cell lung cancer with and without prior exposure to PD-1/PD-L1 inhibitors: Anti-tumor activity will be assessed by objective response rate (ORR, complete response and partial response) using RECIST criteria (version 1.1)
 
Secondary Objectives:
 
(1) To assess the efficacy of the combination treatment of metformin with nivolumab according to depth, duration, and persistence of response, disease control rate (DCR; CR, PR, and SD at 24 weeks), progression-free survival (PFS), and overall survival (OS) in patients with non-small cell lung cancer with and without prior exposure to PD-1/PD-L1 inhibitors using RECIST criteria
 
(2) To assess the efficacy of the combination treatment of metformin with nivolumab according to depth, duration, and persistence of response, ORR, DCR, PFS, and OS in the above population using immune-related RECIST (irRECIST) criteria
 
(3) To assess the safety and tolerability profile of the combination treatment of metformin with nivolumab in the above population using CTCAE version 4.03
 
Exploratory objective:
 
(1) To assess the immune-related tumor and blood biomarkers including T cell markers and their association with treatment response in the above population
 
(2) To assess the dynamic change in both immune and genomic biomarkers in blood that may correlate with response to treatment.

Sample Size	
Up to 51 patients (minimum of 21 patients)
 
Based on optimal Simon two stage design;
 
 - Arm A: If stopped earlier 9 patients will be enrolled to arm A, if continued, 24 patients will be enrolled. - Arm B: If stopped earlier 12 patients will be enrolled to arm B, if continued 25 patients will be enrolled. 
Total maximum number of evaluable patients=49
 
Given possible inevaluable patient and drop out from study, we will aim for 51 patients for total enrollment.
 
This will be a single institution trial with duration of enrollment estimated to be 2 years.
 
Estimated accrual rate will 25.5 per year, approximately 2 per month.

NU Study Number: NU 16L04
Other Study Number: CA 209-801

Diagnosis & Key Eligibility Criteria	
Study population will consist of patients age 18 or older, Eastern Cooperative Oncology Group (ECOG) performance status 0-2, with histologically confirmed, locally advanced or metastatic non-small cell lung cancer (arm A: naive to single agent PD-1/PD-L1 inhibitors that includes but not limited to durvalumab, pembrolizumab, atezolizumab, nivolumab, avelumab; arm B: refractory to or progressed on one of the above agents; both cases are defined by initial PD or PD following CR, PR, or SD using RECIST criteria.). Patients need to have adequate kidney, bone marrow, and liver functions, and a measurable disease according to Response Evaluation Criteria of Solid Tumors (RECIST).
 
Patient should not have received metformin within 6 months from the consent date. (Arm B: Patients who were on metformin while on PD-1/PD-L1 inhibitors will be excluded). Patients with exposure to prior immunotherapy, including combination treatment with PD-1/PD-L1 inhibitors are excluded from arm A. Immunotherapy agents include but are not limited to interleukin-2 and other immune checkpoint antagonist targeting CTLA-4, LAG-3, TIM-3, KIR etc. and/or agonists targeting OX40, ICOS, CD137, etc. Also, patients who are intolerant to PD-1/PD-L1 inhibitors or metformin are also excluded. Prior cancer vaccine treatments are permitted for both arms. Of note, patients with prior exposure to single agent PD-1/PD-L1 inhibitors or combination treatment with PD-1/PD-L1 inhibitor and chemotherapy (such as carboplatin, pemetrexed, and pembrolizumab) are eligible for enrollment in arm B.
 
Patients cannot have a history of clinically significant autoimmune diseases or a syndrome that requires systemic steroids (>10mg prednisone or equivalent, premedication for contrast allergy is permitted) or immunosuppressive agents. Autoimmune diseases include but are not limited to autoimmune hepatitis, systemic lupus erythematosus, rheumatoid arthritis, inflammatory bowel disease, multiple sclerosis, vasculitis, or glomerulonephritis. Vitiligo, alopecia, hypothyroidism on stable doses of thyroid replacement therapy, psoriasis not requiring systemic therapy within the past 3 years is permitted. Short-term steroid premedication for contrast allergy is permitted. Metastatic brain parenchymal disease must have been treated and patient must be off steroids for at least two weeks. Patients with another primary malignancy within 2 years prior to starting study treatment with the exception of adequately treated basal cell carcinoma, squamous cell carcinoma or other non-melanomatous skin cancer, or in-situ carcinoma of the uterine cervix, or any local cancers that are deemed to be cured from investigator's point of view.

Treatment Plan	
Patients will start metformin (Glucophage XR) at 1,000mg by mouth once daily during a 7-day induction period prior to starting nivolumab Cycle 1 Day 1 (1 cycle = 28 days). The dose will be increased by 500mg every 7 days (C1D1 and C1D8) until reaching the target dose of 2000mg. Nivolumab will be administered at a fixed dose of 240 mg IV every 14 days during Cycle 1-4 (Day 1 & 15) and 480mg IV every 28 days starting with Cycle 5 Day 1. Treatment will continue until disease progression confirmed by RECIST criteria v1.1, intolerable toxicity or withdrawal of consent. Imaging by CT or MRI will be scheduled every 2 cycles (8 weeks).

NU Study Number: NU 16L04
Other Study Number: CA 209-801

Statistical Methodology	
Accounting for invaluable patients and dropouts, up to 51 patients (Arm A=24, Arm B=25) will be entered into the trial based on optimal Simon two stage design as below.
 
Arm A: In the first stage, 9 patients will be entered. If no patients show a response, then the trial will be terminated due to inactivity of the treatment. If 1 or more of 9 show a response, then an additional 15 patients will be added. If 2 or fewer of 24 show a response, then the trial will conclude that the response rate could be as low as 5%. If 3 or more respond, then the trial will conclude that the response rate is at least 20%. This design has a 20% chance of falsely concluding the rate is 5% (false negative Type II error rate = 20%, or power = 80%), and a 10% chance of falsely concluding that the rate is 20% (false positive Type I error rate = 10%). There is a 63% probability of early termination of the trial when the true response rate is 5%.
 
Arm B: In the first stage, 12 patients will be entered. If 2 or fewer patients show a response, then the trial will be terminated due to inactivity of the treatment. If 3 or more of 12 show a response, then an additional 13 patients will be added. If 7 or fewer of 25 show a response, then the trial will conclude that the response rate could be as low as 20%. If 8 or more respond, then the trial will conclude that the response rate is at least 40%. This design has a 20% chance of falsely concluding the rate is 20% (false negative Type II error rate = 20%, or power = 80%), and a 10% chance of falsely concluding that the rate is 40% (false positive Type I error rate = 10%). There is a 56% probability of early termination of the trial when the true response rate is 5%.

--------------------------------	---

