Group A and Group B will address two clinical questions. Group A is designed to assess possible synergistic effect of the combination treatment in immunotherapy naïve patients whereas group B is designed to determine whether the combination treatment of metformin with immunotherapy can overcome resistance to single agent PD-1/PD-L1 inhibitors.

Group A: In order to demonstrate synergy in anti-tumor effect, ORR of the combination treatment will be compared to that of historical control (20%) reported in phase 3 single agent nivolumab trials in lung cancer (CheckMate057 and CheckMate017). Optimal Simon's two stage design will be used with target ORR of 40% versus control ORR of 20% (type 1 error rate of 0.1 and power of 0.8)

Group B: In order to find signal in patients with prior exposure to single agent PD-1/PD-L1 inhibitors, ORR of the combination treatment will be described. Optimal Simon's two stage design will be used with target ORR of 20% versus control ORR of 5% (type 1 error rate of 0.1 and power of 0.8).

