3.1 Inclusion Criteria

- 3.1.1** Patients must have histologically confirmed, locally advanced or metastatic stage IV or non-resectable stage III non-small cell lung cancer (NSCLC).
- 3.1.2** Patients may have received any number and type of prior treatment regimens for their NSCLC (aside from patients in Arm A, who cannot have had PD-1/PD-L1 inhibitors).
- 3.1.3** Arm A: patients must be treatment naive to PD-1/PD-L1 inhibitors including but not limited to durvalumab, pembrolizumab, atezolizumab, nivolumab, and avelumab.

Arm B: patients' tumor must be either refractory to or progressed on one of the above agents.

NOTE: Prior treatment may include any number of PD-1/PD-L1 inhibitor therapies given as either a single-agent or in combination with chemotherapy..

NOTE: Patients must be eligible to receive the next line of therapy and not be suspected of having pseudoprogression. Both cases are defined by initial PD or PD after CR, PR, or SD using RECIST criteria, respectively.

NU Study Number: NU 16L04
Other Study Number: CA 209-801

3.1.4 Patients must have measurable disease according to the standard RECIST version 1.1.

NOTE: CT scans or MRIs used to assess the measurable disease must have been completed with 28 days prior to the study drug initiation.

3.1.5 Patients need to have adequate kidney, bone marrow, and liver functions ≤ 14 days of registration as specified below:

absolute neutrophil	$\geq 1,000/\text{mCL}^*$
platelets	$\geq 50,000/\text{mCL}^*$
hemoglobin	$\geq 8 \text{ g/dL}$
total bilirubin	≤ 1.5 times the institutional upper limit of normal (ULN) (or ≤ 3 times ULN in case of liver metastasis or Gilbert Syndrome)
AST(SGOT)/ALT(SPGT)	$\leq 2.5 \times$ institutional ULN (or ≤ 5 times ULN in case of liver metastasis)
creatinine	$\leq 1.4 \text{ ng/mL}$ for females; $\leq 1.5 \text{ ng/mL}$ for males** ng/ml

*Transfusion and/or growth factor are permitted within any timeframe.

**Patients with creatinine $\leq 2.0 \text{ ng/mL}$ may still be eligible if in the opinion of the investigator, the benefits of treatment outweigh the risks.

3.1.6 Patients must be age ≥ 18 years; both male and female are eligible.

3.1.7 Patients must exhibit an ECOG performance status of ≤ 2 .

3.1.8 Patients must have the ability to understand and the willingness to sign a written informed consent prior to registration on study.

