3.2 Exclusion Criteria

3.2.1 Both arms: Patients should not have received metformin within 6 months prior to registration.

Arm B: Patients who were on metformin while on PD-1/PD-L1 inhibitors are not eligible.

3.2.2 Patients should not have received prior immunotherapies (exception: prior PD-1/PD-L1 inhibitors are allowed for arm B only).

NOTE: Prior cancer vaccine treatments are permitted. For arm B, exposure to PD-1/PD-L1 inhibitors given as either a single agent or in combination with chemotherapy are allowed ≥ 14 days from registration.

NOTE: Immunotherapies include but are not limited to interleukin-2 and other immune checkpoint antagonist targeting CTLA-4, LAG-3, TIM-3, KIR etc. and/or agonists targeting OX40, ICOS, CD137, etc.

3.2.3 Patients who are intolerant to PD-1/PD-L1 inhibitors and/or metformin are excluded.

3.2.4 Patients with active autoimmune disease or history of autoimmune disease that might recur, which may affect vital organ function or require immune suppressive treatment including chronic prolonged systemic corticosteroids (defined as corticosteroid use of duration one month or greater), should be excluded. These include but are not limited to patients with a history of:

- immune related neurologic disease
- multiple sclerosis
- autoimmune (demyelinating) neuropathy
- Guillain-Barre syndrome
- myasthenia gravis
- systemic autoimmune disease such as SLE
- connective tissue diseases
- scleroderma
- inflammatory bowel disease (IBD)
- Crohn's
- ulcerative colitis
- patients with a history of toxic epidermal necrolysis (TEN)
- Stevens-Johnson syndrome
- anti-phospholipid syndrome

NOTE: Subjects with vitiligo, type I diabetes mellitus, residual hypothyroidism due to autoimmune condition only requiring hormone replacement, psoriasis not requiring systemic treatment, or conditions not expected to recur in the absence of an external trigger are permitted to enroll.

NU Study Number: NU 16L04
Other Study Number: CA 209-801

3.2.5 Patients are ineligible who have any condition requiring systemic treatment with corticosteroids (>10mg daily prednisone equivalents) or other immunosuppressive medications ≤14 days prior to registration.

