8. The same modality used at baseline should be used throughout for imaging. CT imaging with contrast will occur every 2 cycles starting with Cycle 3 Day 1 (\pm 7 days) and should include chest, abdomen, and pelvis. Neck will be included only if measurable lesions are present. Metformin should be held prior to scans per each institutional protocol. Tumor measurements will be performed using RECIST 1.1. Progressive Disease (PD) must be confirmed by repeat scan within 8 weeks at least after 4 weeks. Patients with a known history of CNS disease must have CNS imaging at screening to rule out activity.
9. Patients will undergo a fresh tissue biopsy prior to study enrollment, unless deemed to be clinically inappropriate per PI. If not feasible, archived tissue will be used (if available).
10. The maximum time interval between registration and the first dose of study drug will be 14 days
11. Nivolumab will be given as follows:
Cycle 1-4: 240mg IV over 30 minutes (-5 / +15 minutes) every 14 days (Day 1 & 15, \pm 3 days)
Cycle 5+: 480mg IV over 60 minutes (-10 / +15 minutes) every 28 days (Day 1, \pm 3 days) until disease progression, intolerance, or withdrawal of consent.
12. Metformin will be dispensed Day 1 of each cycle. Dosing will begin at 1,000mg po once daily and escalate by 500mg every 7 days until the final dose of 2,000mg is reached. Patients will return unused drug and drug bottles at each study visit and will maintain a drug diary to track compliance.
13. The end of treatment visit should occur 30 days after the last dose of study treatment (+/- 7 days) or before starting another line of treatment, whichever comes first.
14. Correlatives from peripheral blood will be collected for all patients at Induction Day 1, C1D1, C3D1, and at the EOT. Biopsy samples (fresh or archived) will be collected for all patients if possible. See separate lab manual for specifications. See section 9.0 for details.
15. Metformin monotherapy will be given at 1,000mg PO QD during the 7-day Induction period, prior to starting nivolumab on Cycle 1 Day 1.
16. After patients come off treatment they will be followed up at 3, 6, 9, and 12 months (\pm 7 days) and then every 6 months (\pm 14 days) for 3 years for survival and progression of disease via either clinic visits or phone calls.

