6.2 Immune-related RECIST (irRECIST)

- 6.2.1 In addition to above, tumor response will be assessed by the irRECIST for investigational purposes, not assessment of primary objective or treatment decisions.¹³ In RECIST v1.1, the appearance of new lesions indicates PD. However, in irRECIST, new measurable lesions are incorporated in the tumor burden, which is used to determine irPD, immune-related partial response (irPR), and immune-related complete response (irCR). New nonmeasurable lesions preclude irCR. Under RECIST v1.1, there is no confirmation for PD. Under irRECIST, responses and irPDs must be confirmed by consecutive scans at least 4 weeks apart, assuming no clinical deterioration. We will define immune-related clinical benefit rate as immune-related stable disease (irSD), irPR, or irCR.

NU Study Number: NU 16L04
Other Study Number: CA 209-801

Table 6-1: Immune-related Response Evaluation Criteria: Overall Response

Tumor Burden (Baseline and New)	Non-Target Lesions (Baseline and New)	Response
Disappearance of non-nodal lesions. All pathologic lymph nodes <10 mm (short axis)	Disappearance of non-nodal lesions. All pathologic lymph nodes < 10 mm (short axis)	irCR
≥30% decrease from baseline	Any	irPR
≥20% increase from nadir and at least 5 mm	Any	irPD
Neither sufficient decrease to qualify for PR, nor sufficient increase to qualify for PD	Any	irSD
Disappearance of all non-nodal lesions. All pathologic lymph nodes <10 mm	Any other than disappearance of all non-nodal lesions and reduction of pathologic lymph nodes <10 mm	irPR
Not all evaluated	Any	irNE

irCR = immune-related complete response; irPD = immune-related progressive disease; irPR = immune-related partial response; irNE = immune-related not evaluable; irSD = immune-related stable disease;

-Tumor burden is the sum of single diameters (short axis for nodal lesions, longest diameter for other lesions) for the target lesions. In subsequent scans, the diameters of new measurable lesions are added to the tumor burden.

-Best overall response based on 2 consecutive measurements at least 4 weeks apart.

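### Arm B does not require the qualifying PD on a prior PD-1/PD-L1 inhibitor to be confirmed, so an unsuspected pseudoprogressor could be counted as resistance overcome

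*Combined protocol and SAP*

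**What the plan says.** **Entry to Arm B.** The Study Summary (Diagnosis & Key Eligibility Criteria) covers refractory disease and later progression together: "both cases are defined by initial PD or PD following CR, PR, or SD using RECIST criteria". Section 3.1.3 repeats this and adds a note: "Patients must be eligible to receive the next line of therapy and not be suspected of having pseudoprogression". Neither place asks for a second scan, an interval or a minimum prior exposure. Section 3.2.2 says that prior PD-1/PD-L1 inhibitors are "allowed ≥ 14 days from registration".

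**Progression on study.** Table 5-1, footnote 8, says "Progressive Disease (PD) must be confirmed by repeat scan within 8 weeks at least after 4 weeks". The Study Summary (Treatment Plan) says "Treatment will continue until disease progression confirmed by RECIST criteria v1.1". Section 4.4 links the repeat scan to continuing treatment after a first PD. Section 6.2.1, in contrast, says "Under RECIST v1.1, there is no confirmation for PD" and treats confirmation as an irRECIST rule.

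**Baseline and response.** Screening scans may be up to 28 days old at registration (Table 5-1, footnote 2) or at first study drug (3.1.4). PR is a fall of at least 30% from the baseline sum (6.1.7). Section 10.3 uses the best response before progression. No confirmation of response is stated for the RECIST v1.1 primary endpoint.

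**Purpose.** Section 1.3.2 says that Group B asks whether adding metformin can overcome resistance to PD-1/PD-L1 inhibitors.

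**The concern.** Every Arm B response is meant to show that resistance was overcome, so the arm's answer depends on entrants having been resistant. A first PD on a checkpoint inhibitor can be pseudoprogression. The protocol recognises this twice, in the 3.1.3 note and in the on-study repeat scan. At entry, however, detection rests on judgement alone.

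A patient whose pseudoprogression nobody suspected would go from one PD-1/PD-L1 inhibitor to nivolumab plus metformin. The lesions could then regress for reasons unrelated to metformin. With no control arm, the design cannot tell that patient from a true success. Under a low null rate, one or two such patients can change the decision.

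**Working it through.** **1. Can it happen under the text?**

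- The qualifying PD may rest on one scan: 3.1.3 asks for RECIST PD, and 6.2.1 says RECIST v1.1 PD is not confirmed.
- The prior inhibitor may be as recent as 14 days before registration, and the baseline scan may be up to 28 days before it. A scan taken near the last prior dose can therefore be both the PD scan and the baseline.
- If the sum at that scan is a fraction g above its pre-progression value, PR is reached at 0.70 × (1 + g) of that value. For g = 20% this is 0.70 × 1.20 = 0.84; for g = 40%, 0.70 × 1.40 = 0.98. These values of g are illustrative.

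**2. Which decision rule?**

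Section 1.3.2 gives Group B a 5% control rate and a 20% target. Section 10.3 also gives Group B 5%, but with a 40% target. The Study Summary and section 10.2 attach the 5%/20% design to Arm A and the 20%/40% design to Arm B. Both rules are therefore worked through.

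With stage sizes n1 and n, and limits r1 and r:

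Pr(pass) = Σ over x = r1+1 to n1 of b(x; n1, p) × Pr[Bin(n − n1, p) ≥ r + 1 − x]

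The plan's own figures reproduce:

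| Rule (r1/n1, r/n) | Type I error | Power | Early stop at the null |
|---|---|---|---|
| 0/9, 2/24 (5% v 20%) | 9.3% | 80.5% | 63.0% |
| 2/12, 7/25 (20% v 40%) | 9.9% | 81.5% | 55.8% |

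The 56% early-stopping figure printed for Arm B is labelled as holding at a 5% true rate. It holds at 20%; at 5% the figure is 98.0%.

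**3. Adding unsuspected pseudoprogressors.**

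Let c be their share of entrants and q the chance that one of them scores PR. Neither is in the documents; both are assumptions. If the combination does no better than the null rate p0 in truly resistant patients, the observed rate is p = p0(1 − c) + qc. For c = 5%:

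- p0 = 5%: 0.0475 + 0.025 = 0.0725 (q = 50%); 0.0475 + 0.05 = 0.0975 (q = 100%).
- p0 = 20%: 0.19 + 0.025 = 0.215 (q = 50%); 0.19 + 0.05 = 0.24 (q = 100%).

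Chance of passing, for q = 50% to 100%:

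| c | 0/9, 2/24; p0 = 5% | 2/12, 7/25; p0 = 20% | 2/12, 7/25; p0 = 5% |
|---|---|---|---|
| 0% | 9.3% | 9.9% | 0.002% |
| 2% | 13.4%-18.6% | 11.3%-14.0% | 0.006%-0.02% |
| 5% | 20.5%-35.0% | 13.7%-21.6% | 0.02%-0.17% |
| 10% | 33.5%-60.6% | 18.2%-37.1% | 0.14%-1.9% |

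As a count: 5% of 24 is 1.2 patients. Exactly one certain pseudo-responder among 24 raises the 0/9, 2/24 false-positive rate from 9.3% to 26.0%; two raise it to 56.0%.

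**The case against.** **A safeguard exists.** A reader might infer that one unconfirmed scan is the whole test of resistance. The documents do not support that. Section 3.1.3 excludes suspected pseudoprogression and requires that patients be ready for a next line of therapy. Appendix E shows that the pseudoprogression note was added at the IRB's request, so the risk was considered. This stands: only unsuspected cases remain.

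**The larger figures depend on a rule not printed for Arm B.** A reader might take 35% or 60% as the Arm B error rate. The 0/9, 2/24 rule is printed only for Arm A. Under the rule printed for Arm B, with a true 5% rate in resistant patients, the chance of passing is at most 1.9% even at c = 10%. This stands, and it is why both rules are shown. Still, from its own 20% null the printed Arm B rule also loses error control, only more slowly.

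**The inputs are assumed.** The documents give neither c nor q. PD by new lesions need not enlarge the target sum, and at g = 20% a PR still needs a 16% fall below the pre-progression value. The 5% null has no stated source, so it might already allow for such patients; nothing shows that it does or does not.

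**The on-study standard is not uniform.** Footnote 8 and the Study Summary call for confirmation, 6.2.1 says RECIST v1.1 has none, and 4.4 uses the repeat scan mainly to decide on continuing treatment. So it cannot be said that the protocol consistently rejects an unconfirmed PD as an endpoint. The narrower contrast remains: a repeat scan is required somewhere on study and nowhere at entry.

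**Requiring confirmation at entry could delay treatment** in patients with progressing NSCLC. This stands as a reason not to insist on it.

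**Conclusion.** The point holds as a gap in interpretability. The text lets an unsuspected pseudoprogressor enter Arm B, use the PD scan as baseline and be scored a responder, and nothing in the planned analysis would show it.

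The size cannot be derived from the documents. As an illustration at c = 5% with q from 50% to 100%, the false-positive rate goes from 9.3% to 20.5%-35.0% under 0/9, 2/24 at a 5% null, or from 9.9% to 13.7%-21.6% under 2/12, 7/25 at a 20% null. If the printed Arm B rule is applied to a population whose true rate is 5%, the effect is negligible. All of this assumes independent patients and a null rate that does not already include such cases. The documents do not support a claim that the Arm B result would be invalid, or that entry has no protection against pseudoprogression.

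**What to change.** 1. Add a field to the registration eCRF for Arm B: was the qualifying PD confirmed by a second scan at least 4 weeks after the first PD scan (yes, no, unknown)? State that the screening scan may serve as the second scan.
2. In section 10.3, prespecify a sensitivity analysis of the Arm B ORR with exact confidence intervals, with numerator and denominator both restricted to patients whose qualifying PD was confirmed. Restricting only the numerator would bias the rate downward.
3. Beside the primary Arm B decision, list each responder's confirmation status.
4. Reconcile 3.1.3 with footnote 8, and footnote 8 with 6.2.1. Whether confirmation should become an entry requirement is for the sponsor to decide.
5. Resolve the conflict between 1.3.2/10.3 and the Study Summary/10.2 over which design belongs to which arm; until then the effect on Arm B's error rate cannot be fixed to one rule.

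Items 1 to 3 cost one eCRF field, one table row and a short listing. The restricted estimate will be less precise because it uses fewer patients. The primary analysis, eligibility and time to treatment are unchanged.
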